4 STUDY OBJECTIVES

The objectives of this study are to assess the safety, and efficacy, of venetoclax in combination with AZA/DLI in patients with myeloid neoplasms in relapse after allo hematopoietic stem cell transplantation.

Phase I:

- Assess the safety profile of venetoclax in combination with AZA/DLI
- Determine the recommended Phase II dose (RPTD)

Phase II: To determine the efficacy of venetoclax in combination with AZA/DLI

5 STUDY ENDPOINTS

5.1 Primary endpoint

Phase I: To determine toxicity profile and safety of the combination

Phase II: Overall hematological response rate of venetoclax in combination with AZA/DLI

Response assessment will be performed according to modified IWG 2006 criteria for MDS and according European LeukemiaNet criteria for AML.

5.2 Secondary endpoints

- ✓ Toxicity as measured by NCI CTCAE 5.0
- ✓ Acute and chronic GVHD rate
- ✓ Duration of response (DOR)
- ✓ Overall survival (OS)
- ✓ Progression-free survival (PFS)
- ✓ Event-free survival (EFS)

5.3 Exploratory endpoint

- ✓ Study the correlation between patient overall mutational status before treatment and response
- ✓ The prognostic impact on outcome of MRD

6 INVESTIGATIONAL PLAN

6.1 Overall design

This is an open label multicenter phase I/II study. Patients will be treated with venetoclax during 14 days in combination with AZA at 75 mg/m²/day for 5 days for each cycle or 50 mg/m²/day for 5 days each cycle if relapse occurred less than 4 months after allo SCT.

Patients who meet eligibility criteria will be administered VENETOCLAX orally at starting dose in phase I part and at MTD in phase II part on days 1-14 in combination with AZA at 75 mg/m²/day for 5 days on days 1-5 for each cycle or 50 mg/m²/day for 5 days each cycle if relapse occurred less than 4 months after allo SCT.

Following cycles must be administered on day 28 or delayed until day 42 in cases of hematological toxicity. Each cycle will last 28 days starting on day 1 of each cycle when ANC > 1 G/L and platelet > 50 G/L without transfusion or when recovery of baseline level.

In the phase I part, VENETOCLAX will be given once daily orally on days 1-14 for all cycles at escalating doses starting at Dose Level 1 (defined below) in combination with AZA +/- DLI. Patients will receive at least 8 cycles of VENETOCLAX/AZA/DLI unless progression occurs. Response will be assessed after 4, 6 and 8 cycles. Patients achieving a response (see appendix 11 and 12) will be able to continue on protocol with VENETOCLAX + AZA until 12 cycles maximum then with AZA alone. In the absence of response, patients will stop treatment.

Dose Levels for Treatment in Phase I

Dose Level	VENETOCLAX (mg)	Azacitidine (mg/m ²)
-1	50 mg*	75 (50 if relapse < 4 months)
1 (Starting dose)	100 mg*	75 (50 if relapse < 4 months)
2	200 mg*	75 (50 if relapse < 4 months)
3	400 mg*	75 (50 if relapse < 4 months)

*VENETOCLAX will be given once daily orally during 14 days.

In the phase II part, VENETOCLAX will be given once daily orally on days 1-14 for all cycles at MTD defined in the phase I part of the study in combination with AZA/DLI. Patients will receive at least 8 cycles of VENETOCLAX/AZA/DLI unless progression occurs. Response will be assessed after 4, 6 and 8 cycles. Patients achieving a response (defined below) will be able to continue on protocol with VENETOCLAX + AZA until 12 cycles maximum then AZA alone. In the absence of response, patients will stop treatment.

Ramp-up** will be performed at the beginning of cycle 1:

Dose Level	VENETOCLAX D1C1	VENETOCLAX D2C1	VENETOCLAX D3C1 and beyond
-1	10 mg*	20 mg*	50 mg*
1 (Starting dose)	20 mg*	50 mg*	100 mg*
2	50 mg*	100 mg*	200 mg*
3	100 mg*	200 mg*	400 mg*

*VENETOCLAX will be given once daily orally.

**Therapy with CYP3A inhibitor are not allowed during the ramp up.

DLI will be infused every two cycles (C2, C4, C6, C8) at day 15 in absence of GVHD as follows, and at least 8 weeks after immunosuppressive therapy discontinuation. If the chimerism in > 90% recipient, DLI will not be performed.

	DLI dosage
Sibling-Id or Unrelated Donor-Id 10/10	0.5 x 10 ⁷ CD3/kg 1 x 10 ⁷ CD3/kg 0.5 x 10 ⁸ CD3/kg 1 x 10 ⁸ CD3/kg
Unrelated Donor-Id 9/10	1 x 10 ⁶ CD3/kg 5 x 10 ⁶ CD3/kg 1 x 10 ⁷ CD3/kg 0.5 x 10 ⁸ CD3/kg

Patients with Complete Remission (CR), Partial Remission (PR), marrow CR or Hematological Improvement (HI) after 8 Cycles of therapy (IWG 2006 criteria or Cheson et al. criteria for AML) continue on protocol with VENETOCLAX + AZA until 12 cycles maximum then AZA alone. Patients with no response (NR) to treatment will be withdrawn from the protocol after the last treatment Cycle.

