9 CRITERIA FOR MEASUREMENT OF STUDY ENDPOINTS

9.1 Efficacy Outcome Measures

Primary Endpoint:

For MDS patients:

Overall response rate (ORR), defined as the proportion of patients who achieve a CR or PR per proposal for modification of the International Working Group (IWG) criteria for MDS, 2006 (Appendix 11):

1. CR is defined as bone marrow blasts $\leq 5\%$, without persistent dysplasia will be noted with normal maturation of all cell lines peripheral blood: Hgb ≥ 11 g/dL platelets $\geq 100 \times 10^9/L$, ANC $\geq 1.0 \times 10^9/L$, blasts 0%.
2. PR is defined as all CR criteria if abnormal before treatment except for bone marrow blasts decreased by $\geq 50\%$ over pretreatment but still $> 5\%$ cellularity.

For AML patients:

CR Rate, defined as the proportion of patients who achieve a CR per the ELN2017 criteria: CR is defined as BM blasts $< 5\%$, absence of circulating blasts and blasts with Auer rods, absence of extramedullary disease, ANC $\geq 1.0 \times 10^9/L$ (1,000/ μ L); platelet count $\geq 100 \times 10^9/L$ (100,000/ μ L).

Secondary Endpoints:

For MDS patients:

1. Overall improvement rate (OIR), defined as the proportion of patients reaching a CR, Marrow CR, PR, or hematologic improvement (HI) per proposal for modification of the IWG criteria for MDS, 2006 (Appendix 11). Marrow CR is defined as bone marrow blasts $\leq 5\%$ and decreased by 50% over pretreatment. Peripheral blood: if HI responses, they will be noted in addition to marrow CR. HI is defined as:
 - a. Erythroid response (pretreatment, < 11 g/dL) is defined as Hgb increase by ≥ 1.5 g/dL. Relevant reduction of units of red blood cells (RBC) transfusions by an absolute number of at least 4 RBC transfusions/8 weeks, compared with the pretreatment transfusion number in the previous 8 weeks. Only RBC transfusions given for a Hgb of ≤ 9.0 g/dL will count in the RBC transfusion response evaluation.
 - b. Platelet response (pretreatment $< 100 \times 10^9/L$) is defined as absolute increase of $\geq 30 \times 10^9/L$ for patients starting with $> 20 \times 10^9/L$ platelets, and an increase from $< 20 \times 10^9/L$ to $> 20 \times 10^9/L$ and by at least 100%.
 - c. Neutrophil response (pretreatment, $< 1.0 \times 10^9/L$) is defined as at least 100% increase and an absolute increase $> 0.5 \times 10^9/L$

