2. Duration of Response (DOR), defined as time from the date of the first observed PR/CR to the date of the first subsequent documented disease progression or relapse per IWG 2006 criteria, or death from any cause.
3. Progression Free Survival (PFS), for patients with at least a PR, defined as time from the date of the first dose of study treatment to the date of the first documented disease progression or relapse per IWG 2006 criteria, or death from any cause.
4. Overall Survival (OS), defined as time from the date of the first dose of study treatment to the date of death from any cause.
5. Event-Free Survival (EFS) defined as the number of days from the date of the first dose of study drug to the date of earliest disease progression or death of any cause.
6. Rate of bone marrow blast response, defined as the proportion of patients with a reduction in bone marrow blast counts following treatment.
7. Time to AML transformation, defined as time from first treatment dose to the first date in which AML is established.
8. CR Rate, defined as the proportion of participants who achieved a CR per the IWG 2006 Criteria.
9. Rate of HI, defined as the proportion of patients reaching a HI per the IWG 2006 Criteria.

For AML patients:

1. Overall response rate (ORR) including; CR and CRi according to the Diagnosis and Management of AML in Adults: 2017 ELN Recommendations from an International Expert Panel Revised (see Appendix 12) (Döhner et al., 2017)
 - a. CR is defined as bone marrow blasts < 5%; absence of circulating blasts and blasts with Auer rods; absence of extramedullary disease; ANC $\geq 1.0 \times 10^9/L$ (1000/ μ L); platelet count $\geq 100 \times 10^9/L$ (100 000/ μ L)
 - b. CRi is defined as all CR criteria except for residual neutropenia (< $1.0 \times 10^9/L$ (1,000/ μ L)) or thrombocytopenia (< $100 \times 10^9/L$ (100,000/ μ L)).
2. Duration of Response (DOR), defined as time from the date of the first observed CR/CRi to the date of the first subsequent documented disease progression or relapse per IWG 2006 criteria, or death from any cause.
3. Progression Free Survival (PFS) for patients with at least CRi, defined as time from the date of the first dose of study treatment to the date of the first documented disease progression or relapse per IWG 2006 criteria, or death from any cause.
4. Overall Survival (OS) defined as time from the date of the first dose of study treatment to the date of death from any cause.

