Overall survival (OS) will be defined as the number of days from the date of the first dose of study drug to the date of death. Overall survival will be analyzed by Kaplan-Meier methodology. Median OS will be calculated and 95% confidence interval for median OS will be presented. Data from subjects that are alive at the time of analysis will be censored at the date of last study visit or the last known date the subject was alive, whichever is later.

Progression-Free Survival

Progression-free survival (PFS) will be defined as the number of days from the date of the first dose of study drug to the date of earliest disease progression or death due to disease progression or febrile neutropenia. Progression-free survival will be analyzed by Kaplan-Meier methodology. Median PFS will be calculated and 95% confidence interval for median PFS will be presented. All events of disease progression will be included regardless whether the event occurred while the subject was taking the study drug or had previously discontinued the study drug. Refer to Appendix 11 and 12 for the definition of disease progression. If the subject has not experienced disease progression or death, the subject's data will be censored at the date of last disease assessment. Data for subjects without any disease assessments performed after the first dose of study drug will be censored at the time of the first dose of study drug.

Event-Free Survival

Event-free survival (EFS) will be defined as the number of days from the date of the first dose of study drug to the date of earliest disease progression or death of any cause.

Event-free survival will be analyzed by Kaplan-Meier methodology. Median EFS will be calculated and 95% confidence interval for median EFS will be presented. All events of disease progression will be included regardless whether the event occurred while the subject was taking the study drug or had previously

discontinued the study drug. If the subject has not experienced disease progression or death, the subject's data will be censored at the date of last disease assessment. Data for subjects without any disease assessments performed after the first dose of study drug will be censored at the time of the first dose of study drug.

Safety assessments

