Stable disease	Absence of CR _{MRD-} , CR, CR _i , PR, MLFS; and criteria for PD not met	Period of stable disease should last at least 3 mon
Progressive disease (PD)*, †	Evidence for an increase in bone marrow blast percentage and/or increase of absolute blast counts in the blood: 
 • 50% increase in marrow blasts over baseline (a minimum 15% point increase is required in cases with $< 30\%$ blasts at baseline; or persistent marrow blast percentage of $> 70\%$ over at least 3 mo; without at least a 100% improvement in ANC to an absolute level ($> 0.5 \times 10^9/L$ [$500/\mu L$], and/or platelet count to $> 50 \times 10^9/L$ [$50\,000/\mu L$] non-transfused); or • 50% increase in peripheral blasts (WBC \times % blasts) to $> 25 \times 10^9/L$ ($> 25\,000/\mu L$) (in the absence of differentiation syndrome)†; or • New extramedullary disease 	Category mainly applies for older patient given low-intensity or single-agent “targeted therapies” in clinical trials In general, at least 2 cycles of a novel agent should be administered Some protocols may require blast increase in 2 consecutive marrow assessments at least 4 wk apart; the date of progression should then be defined as of the first observation date Some protocols may allow transient addition of hydroxyurea to lower blast counts

CATEGORY	DEFINITION	COMMENT
		“Progressive disease” is usually accompanied by a decline in ANC and platelets and increased transfusion requirement and decline in performance status or increase in symptoms
Relapse		
Hematologic relapse ¶ (after CR _{MRD-} , CR, CR _i)	Bone marrow blasts ≥ 5%; or reappearance of blasts in the blood; or development of extramedullary disease	
Molecular relapse (after CR _{MRD-})	If studied pretreatment, reoccurrence of MRD as assessed by RT-qPCR or by MFC	Test applied, sensitivity of the assay, and cutoff values used must be reported; analyses should be done in experienced laboratories (centralized diagnostics)

ANC, absolute neutrophil count; IDH, isocitrate dehydrogenase; MLFS, morphologic leukemia-free state; WBC, white blood cell.

*The authors acknowledge that this new provisional category is arbitrarily defined; the category aims at harmonizing the various definitions used in different clinical trials.

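### Section 9.1 ends AML duration of response and PFS by the MDS criteria (IWG 2006) although AML is otherwise assessed by ELN 2017, and 10.2 does not settle the conflict

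*Protocol*

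**What the plan says.** **AML response standard.** Section 5.1 assesses response "according European LeukemiaNet criteria for AML". The AML primary endpoint in 9.1 is "CR Rate, defined as the proportion of patients who achieve a CR per the ELN2017 criteria". The introduction to 10.2 also names ELN 2017 for AML, and Appendix 12 sets those criteria out.

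**AML end events in 9.1.** Secondary endpoint 2 (DOR) runs from the "first observed CR/CRi to the date of the first subsequent documented disease progression or relapse per IWG 2006 criteria", or death. Endpoint 3 (PFS) uses the same progression or relapse rule. Appendix 11 presents IWG 2006 as the MDS criteria.

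**Section 10.2, not split by disease.** Overall response is CR, mCR, PR or HI. DOR starts at the first of these and ends at PD. For PFS the text says "Refer to Appendix 11 and 12 for the definition of disease progression". EFS, here and in 9.1, names no criteria set for progression.

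**Section 6.1.** The phase I paragraph reads "Patients achieving a response (see appendix 11 and 12) will be able to continue on protocol". The list further down admits CR, PR, "marrow CR or Hematological Improvement (HI) after 8 Cycles of therapy (IWG 2006 criteria or" an author-named AML set.

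**The concern.** DOR and PFS are listed secondary endpoints, and efficacy is judged by the investigator. In 9.1 an AML response begins on one scale (CR and CRi are ELN categories) and ends on another (the MDS rules). An investigator who follows 9.1 and one who follows Appendix 12 can give the same patient different event dates. Section 10.2 does not decide between them. It points progression for PFS to both appendices without assigning either to a disease, and its response list does not match the AML list in 9.1.

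**Working it through.** The plan gives no figure to reproduce, so the check compares the rules and computes their marrow thresholds.

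**Inputs**, with b the pretreatment marrow blast percentage (inclusion criterion 1: below 30%):

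- *ELN hematologic relapse* (Appendix 12): marrow blasts of 5% or more, "reappearance of blasts in the blood; or development of extramedullary disease".
- *ELN PD, marrow* (Appendix 12): a 50% increase over baseline, and at least 15 points if baseline is below 30%. Threshold = max(1.5b, b + 15). For b < 30, 0.5b < 15, so it is always b + 15.
- *IWG relapse, marrow* (Appendix 11): return to b.
- *IWG progression, marrow* (Appendix 11): a 50% increase that also passes the category limit (5, 10, 20 or 30%). Threshold = max(1.5b, limit).
- *IWG relapse, blood* (Appendix 11): a fall of 50% or more in granulocytes or platelets, an Hgb fall of 1.5 g/dL or more, or transfusion dependence. No blasts are needed.

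**Marrow thresholds (%)**

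| b | ELN relapse | IWG relapse | IWG progression | ELN PD |
|---|---|---|---|---|
| 12 | 5 | 12 | >20 (1.5 × 12 = 18, so the limit governs) | 27 |
| 15 | 5 | 15 | 22.5 | 30 |
| 25 | 5 | 25 | 37.5 | 40 |
| 29 | 5 | 29 | 43.5 | 44 |

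By marrow, IWG calls relapse later than ELN in each row, but progression earlier.

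**One patient: b = 25%, CR, then 12% marrow blasts.**

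- Appendix 12 relapse: met (12 ≥ 5).
- Appendix 11 marrow relapse, the 9.1 rule: not met (12 < 25).
- Appendix 11 marrow progression, also in 9.1: not met (12 < 1.5 × 25 = 37.5).
- Appendix 12 PD, one reading of the 10.2 DOR end: not met (12 < 25 + 15 = 40).

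**The opposite case.** An AML patient in CR has a sustained fall of half or more in platelets, with no blasts. Appendix 11 calls relapse; Appendix 12 does not. (Appendix 11 exempts transient cytopenias between courses that recover.)

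**Time scale.** Response marrows fall after cycles 4, 6 and 8 and at end of study or premature termination (Appendix 1). An event recognised one scheduled marrow later moves by 2 × 28 = 56 days, or 2 × 42 = 84 days if both cycles are delayed to day 42. This is an illustration, not an estimate of the average shift.

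**Response categories for AML**

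| Category | 9.1 AML ORR | 10.2 OR and DOR start | 6.1 list | In Appendix 12 |
|---|---|---|---|---|
| CR | yes | yes | yes | yes |
| CRi | yes | no | no | yes |
| PR | no | yes | yes | yes |
| mCR, HI | no | yes | yes | no |

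Appendix 12 also lists relapse separately from PD. Read literally, 10.2 therefore does not end an AML response at ELN hematologic relapse.

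**The case against.** The strongest reply is that the damage is limited. The trial has one arm, DOR and PFS are descriptive Kaplan-Meier summaries, and no decision rule or sample size rests on them. The AML primary endpoint is tied to ELN in both 5.1 and 9.1. That is correct and bounds the point, but it does not remove the contradiction.

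Four stronger readings are tempting, and the documents do not support them:

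- *A reader might infer that 9.1 makes AML DOR and PFS too long.* The later marrow relapse threshold suggests this, but the blood-based IWG rules and the lower marrow progression threshold can bring events forward. No net direction can be stated.
- *A reader might infer three competing AML criteria sets.* The set named in 6.1 is never defined, and Appendix 11 carries the same author label for the MDS criteria. Only IWG 2006 and ELN 2017 can be compared.
- *A reader might treat 10.2 as the clean ELN reference that 9.1 violates.* It is not: it uses mCR and HI, omits CRi and stops DOR at PD. In the worked patient, 9.1's marrow relapse at 25% would come before ELN PD at 40%.
- *A reader might infer that 6.1 moves DOR or PFS dates.* It governs who continues treatment after cycle 8 and defines no endpoint date.

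**Conclusion.** The point holds. Section 9.1 states an end rule for AML DOR and PFS that conflicts with the protocol's own AML standard. Section 10.2 compounds this through undivided response categories and an unnamed relapse event. EFS shares the ambiguity because its progression has no stated criteria set. In the worked patient the marrow threshold for ending a response is 5%, 25%, 37.5% or 40%, depending on the rule applied.

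The thresholds assume that Appendix 11's progression categories refer to pretreatment blasts, which the text does not say. If they were read from the remission level (for example 4%, giving 1.5 × 4 = 6%), 12% would already count as IWG progression. The difference on the blood-based rules would remain, as would the mismatch in 10.2.

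The number of AML patients affected and the net shift cannot be derived from the protocol. OS and the ELN standard for the AML primary endpoint in 5.1 and 9.1 are not touched by the 9.1 wording. This should be corrected, but it does not threaten the trial's main decision.

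**What to change.** - **Section 9.1, AML secondary endpoints 2 and 3:** replace the reference to IWG 2006 with ELN 2017 (Appendix 12), hematologic relapse or PD. Leave death as it stands.
- **Section 10.2:** give the response categories and the end events for DOR, PFS and EFS separately for MDS (Appendix 11) and AML (Appendix 12). State that relapse after response is an event, and include CRi where 9.1 counts it for AML.
- **Section 6.1:** the list after cycle 8, the pointer to Appendices 11 and 12 in the same section, and the AML categories in 9.1 disagree. Because 6.1 decides who continues treatment, the sponsor must reconcile these passages; this review does not say which rule should apply.

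The cost of the 9.1 and 10.2 changes is a wording amendment, with no effect on sample size. AML DOR and PFS may become shorter or longer than under the present text.

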6.2 Dose Escalation Guidelines

Subjects in part of phase I will be enrolled into a dose-escalation study, and in 3 expansion cohorts evaluating venetoclax combined with azacitidine in subjects with MDS with myeloid neoplasms (blasts < 30%) in relapse after allo hematopoietic stem cell transplantation.

The dose escalation portion is expected to enroll approximately 9 – 18 subjects.

The first venetoclax dose-level to be evaluated in combination with azacitidine will be 100 mg QD at a dosing duration of 14 days per cycle. A cycle is defined as a time period of 28 days.

For this study, the dose limiting toxicities (DLT) observation period is defined as the first treatment cycle (Cycle 1) of venetoclax combined with azacitidine.

Dose limiting toxicities for dose escalation purposes will be determined based on adverse events that occur during the DLT observation period.

Adverse events occurring after the DLT observation period criteria will also be reviewed and may be taken into consideration for dose escalation decisions.

Any of the following events will be considered a DLT unless the event can be attributed by the investigator to a clearly identifiable cause such as underlying illness or disease progression, concurrent other illness, or concomitant medication:

- ANC $< 1 \times 10^9/L$ (Grade ≥ 3) which does not recover as defined below:
 - o Recovery is defined as an increase in ANC from nadir by $\geq 50\%$ of the reduction from baseline to nadir or any increase to an ANC of $\geq 1 \times 10^9/L$ within 42 days from Day 1 of Cycle 1
 - o Delayed recovery should only be deemed a DLT if due to treatment induced toxicity as confirmed by a bone marrow sample showing an overall bone marrow cellularity of $< 5\%$
- Grade ≥ 3 thrombocytopenia associated with clinically significant bleeding that requires transfusion of platelets over routine or baseline transfusion needs based on investigator opinion
- Grade ≥ 4 non-hematologic toxicity deemed related to venetoclax per investigator opinion.
- Grade 4 infections or complications related to infections (e.g., sepsis) should only be deemed DLTs if due to treatment-induced neutropenia as confirmed by a bone marrow sample showing an overall bone marrow cellularity of $< 5\%$

